8.6. Data Management

This study will collect de-identified data. No patient identifiable information including names or medical record number will be collected in the eCRF. For variables that may contain potentially identifiable information such as number of years in practice, ranges or categories will be used rather than collecting specific values. Furthermore, physicians extracting the data will not retain a decoding key so that the data cannot be linked back to an individual. Lastly, the identity of physicians participating in this study will not be known to AG, Medefield, or Pfizer.

De-identified data collected from the physicians by the physician panel vendor will be transferred to AG over a secured and encrypted network for analysis, and stored in secure servers accessible only by designated personnel working on the project within AG. The minimum retention time will meet the strictest standard applicable for the study, as dictated by the applicable guidelines or applicable laws or regulations.

8.7. Data Analysis

8.7.1. Analysis of Physician and Patient Characteristics

Baseline patient demographic and clinical characteristics will be summarized overall and by type of IO therapy given in combination with axitinib. In addition, physician characteristics will be described. Continuous variables will be summarized with mean (\pm standard deviation [SD]) and median (interquartile range [IQR]) values, while categorical variables will be summarized with frequency distributions.

8.7.2. Analysis of AEs

Type and seriousness of AEs will be tabulated and described using frequency and proportions, separately by type of therapy (ie, type of IO therapy given in combination with axitinib). In addition, the proportion of patients who experienced repeated AEs of the same type will be summarized overall and by type of AE. For each type and seriousness of AE, time from index date to onset of AEs will be summarized using means (\pm SD) and medians (IQR). Furthermore, the time between the first AE and the first repeated AE of the same type will be calculated.

8.7.3. Description of Management Strategies for AEs

Among patients with advanced RCC who developed AEs while receiving axitinib/IO combination therapy, descriptive analyses will be conducted to characterize management strategies used for AEs including repeated AEs of the same type, overall and by type and seriousness of the AEs. Frequencies and proportions will be used to describe the various management strategies related to axitinib and other therapies (eg, IO agents). The proportion of patients using multiple management strategies will also be described. Among patients whose AEs were managed with axitinib dose reduction, the average dose reduction will be described using the absolute and percentage change. Duration of treatment interruption will be summarized using means (\pm SD) and medians (IQR).

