7. RESEARCH QUESTION AND OBJECTIVES

The specific objectives of the study are as follows:

1. Describe incident AEs experienced among patients with advanced RCC who received first-line axitinib in combination with IO therapies.
 - Type and seriousness of AEs (ie, diarrhea, fatigue, hypertension, nausea, palmar-plantar erythrodysesthesia [hand-foot syndrome]).

- Proportion of patients who experienced repeated AEs.
- Time from treatment initiation to AE onset, overall and by type and seriousness of AEs.

2. Among patients with advanced RCC who developed incident AEs while receiving first-line axitinib in combination with IO therapies, characterize and describe management strategies for AEs, stratified by type and seriousness of AEs.

- Proportion of patients who used each of the following management strategies:
 - No action for axitinib and IO therapy;
 - No action for axitinib, but treatment modification for IO therapy (ie, treatment interruption, treatment discontinuation);
 - Axitinib dose reduction, but no action for IO therapy;
 - Axitinib treatment interruption, but no action for IO therapy;
 - Axitinib treatment discontinuation, but no action for IO therapy;
 - Axitinib dose reduction, and treatment modification for IO therapy;
 - Axitinib treatment interruption, and treatment modification for IO therapy;
 - Axitinib treatment discontinuation, and treatment modification for IO therapy.
- Average axitinib dose reduction (absolute and percentage change), where applicable.
- Duration of treatment interruption, where applicable.

3. Assess the frequency of and time to AE resolution (from AE onset and initiation of management strategy, separately) among patients with advanced RCC who developed incident AEs while receiving first-line axitinib in combination with IO therapies according to different management strategies implemented, stratified further by type and seriousness of AEs, as allowed by sample size.

[figure not shown]
The above objectives will also be conducted for repeated AEs of the same type.

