8. RESEARCH METHODS

8.1. Study Design

A retrospective physician panel-based chart review study in the US will be conducted. The index date will be defined as the initiation of first-line axitinib (used in combination with IO therapy) on or after May 2019, which marks FDA approval of axitinib in combination with avelumab for first-line advanced RCC treatment. The baseline period will be defined as the 12-month period prior to the index date. The observation period will be defined as the time from index date to the earliest of initiation of a second line therapy, death, loss to follow-up, or date of chart abstraction. During the observation period, onset, management, and resolution of AEs will be assessed. The study design scheme is depicted in Figure 1.

Figure 1. Study Design Scheme

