8.2. Setting

8.2.1. Inclusion Criteria

Physicians meeting the following criteria will be invited to participate in the chart review study:

- Specialty in oncology.
- Access to complete medical records for at least one patient with advanced RCC who meets the patient eligibility criteria.

Eligible oncologists will be asked to select up to three patients meeting the following criteria for inclusion in the chart review study:

- Confirmed diagnosis with advanced RCC.
- Treated with first-line axitinib/IO combination therapy at or after diagnosis.
- Experienced at least one AE (ie, diarrhea, fatigue, nausea, hypertension, and palmar-plantar erythrodysesthesia [hand-foot syndrome]) while treated with axitinib/IO combination therapy.

- Age 18 years or older at the time of advanced RCC diagnosis.
- Initiated axitinib/IO combination therapy at least 3 months prior to the start date of medical chart abstraction to ensure sufficient follow-up time.

In the event that an oncologist has more than three eligible patients, the electronic case report form (eCRF) will have an underlying program that requires the oncologist to select patient charts based on a randomized sequence of letters. Specifically, the program will produce a random letter and request the oncologist to pull the first eligible patient chart with the last name that corresponds to the random letter. If there are no eligible patients whose last name begins with the first letter in the sequence, then the next letter in the order of the sequence will be shown. The random process will repeat for each new patient chart to be completed by the oncologist, until chart abstraction is completed for three eligible patients or until the physician has identified all eligible patients.

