8.3.4. Management Strategies for AEs

The following variables, to the extent they are available, will be assessed during the observation period:

- Type of management strategy:
 - No action for axitinib and IO therapy;

- No action for axitinib, but treatment modification for IO therapy (ie, treatment interruption, treatment discontinuation);
- Axitinib dose reduction, but no action for IO therapy;
- Axitinib treatment interruption, but no action for IO therapy;
- Axitinib treatment discontinuation, but no action for IO therapy;
- Axitinib dose reduction, and treatment modification for IO therapy;
- Axitinib treatment interruption, and treatment modification for IO therapy;
- Axitinib treatment discontinuation, and treatment modification for IO therapy.
- Treatment modification for axitinib:
 - Date(s) of dose reduction;
 - Modified dosage of axitinib;
 - Date(s) when treatment was halted and reinitiated;
 - Date(s) treatment was discontinued.
- Treatment modification for IO therapy:
 - Date(s) when treatment was halted and reinitiated;
 - Date(s) treatment was discontinued.

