8.7.4. Analysis of Resolution of AEs

The proportion of patients achieving resolution of AEs will be described, overall and by type and seriousness of the AEs. The time to resolution from AE onset and from initiation of management strategy will be calculated for all AEs experienced including repeated AEs. The time to resolution of AE (from the onset of AE and from the initiation of management strategies) will be separately estimated using Kaplan-Meier analysis; median time to event will be reported. Analyses will be conducted separately by type of management strategy.

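### Duration of treatment interruption is to be summarised with plain means and medians, with no rule for interruptions still open when observation ends, so the summary leans short by an amount the documents do not fix

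*Combined protocol and SAP*

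**What the plan says.** Objective 2 in section 7 lists the quantity as an output: "Duration of treatment interruption, where applicable". Section 8.7.3 gives the method: "Duration of treatment interruption will be summarized using means" with SD, and medians with IQR. The data behind it, in section 8.3.4, are "Date(s) when treatment was halted and reinitiated". Discontinuation is listed there separately, with its own date, but no rule divides a long halt from a discontinuation.

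Section 8.1 closes observation at the "earliest of initiation of a second line therapy, death, loss to follow-up, or date of chart abstraction". Section 8.2.1 sets the minimum time on study through the criterion "Initiated axitinib/IO combination therapy at least 3 months prior to the start date of medical chart abstraction", with a minimum of 3 months, and section 8.1 accepts index dates "on or after May 2019".

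For the neighbouring duration, time to AE resolution, section 8.7.4 says that it "will be separately estimated using Kaplan-Meier analysis". Neither section 8.7.3 nor the limitations in section 8.9 mentions interruptions that have not ended.

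**The concern.** A duration computed as restart date minus halt date exists only when there is a restart. If observation closes first, the interruption is open: its length is known only to exceed the time already observed. A plain mean or median cannot use that information. The analyst must leave the interruption out, count it as ending on the last day observed, or treat it as a discontinuation. The first and third remove interruptions that tend to be long. The second keeps them with values that are too small.

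The plan already uses a censoring method for time to resolution, in the same patients over the same observation period. The two durations are therefore handled differently without a stated reason. The study is descriptive, so no test or error rate is affected, but the reported durations are themselves the result for this part of Objective 2.

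**Working it through.** **What the documents give.** They contain no interruption lengths, start times or open share, so there is no planned figure to reproduce. They do bound follow-up. From 1 May 2019 to the start of data collection (30 November 2020) is 19.0 months, and to its end (31 January 2021) 21.1 months. The minimum from initiation to the start of abstraction is 3 months.

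**Assumptions (none from the documents).** Potential follow-up F is uniform from 3 to 20.5 months and ends only at abstraction. Durations are exponential with true median 14, 28 or 56 days, so the mean is m = median / ln 2 = 20.2, 40.4 or 80.8 days. Interruptions start either uniformly over follow-up or at an exponential time averaging 4 or 2 months after index. Duration is independent of when observation ends.

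**Open share, uniform start.** For follow-up F the probability of being open is (m/F)(1 − e^(−F/m)). When m is small against F, its average over F is close to m × ln(20.5/3) / (17.5 × 30.44 days). For m = 20.2 this is 20.2 × 1.922 / 532.7 = 7.3%. Averaging the exact expression gives 7.3%, 14.3% and 26.5% for the three medians.

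**Simulated results.** Shortfall of the plain median against the true median:

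| Start of interruption | True median (days) | Open at end | Completed only | Cut at end of observation |
|---|---|---|---|---|
| Uniform over follow-up | 14 / 28 / 56 | 7% / 14% / 26% | 8% / 15% / 28% | 7% / 13% / 24% |
| Mean 4 months | 14 / 28 / 56 | 2% / 6% / 13% | 3% / 6% / 14% | 2% / 4% / 9% |
| Mean 2 months | 14 / 28 / 56 | 1% / 4% / 10% | 1% / 4% / 12% | 1% / 2% / 5% |

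In the uniform case the completed-only medians are 12.9, 23.9 and 40.5 days, for example 1 − 40.5/56 = 28%. The completed-only means are 18.6, 34.2 and 57.1 days against 20.2, 40.4 and 80.8. Kaplan-Meier with open interruptions censored returns medians of 13.9, 28.1 and 56.0 days on the same data.

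**Earlier ends of observation.** A second set of runs used follow-up of 3 to 20 months and added an independent end from second-line start, death or loss, with a median of 12 months. With starts averaging 4 months and a true mean of 8 weeks (median 5.55 weeks), 15.6% are open. The plain median is 4.64 weeks for completed only (4.64/5.55 − 1 = −16%) and 4.78 weeks if cut (−14%). Kaplan-Meier gives 5.56 weeks. Across all runs in this set (true means of 2 to 13 weeks; added end absent or with a median of 12 or 6 months), the completed-only median is 1% to 34% short. The top of that range needs a true mean of 13 weeks and a 6-month median to the added end.

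**Limit of the check.** These runs treat every end of observation as independent censoring. They show the direction of the error and that censoring removes it under that assumption. They do not test a competing-event analysis.

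**The case against.** The strongest reply is that the plan describes an interruption by a halt and a restart, and lists discontinuation apart. A halt without restart may simply be recorded as a discontinuation, so that section 8.7.3 summarises completed interruptions, a legitimate descriptive quantity. This stands in part: no section says that open interruptions will occur. But no section states that coding rule either, and under it the longer gaps would still leave the summary, which is not labelled as restricted to completed interruptions.

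Second, the size may be trivial. That also stands for short, early interruptions. A reader might take the 8% to 28% of the uniform-start case as the expected error. The documents do not support that: they say nothing about timing, and starts averaging 2 to 4 months give about 1% to 14% for completed only and 1% to 9% if cut. Nor are the longest interruptions always lost: cutting keeps them in, with shortened values.

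Third, a reader might infer that a short bias serves the study's stated aim of showing low treatment burden. Section 6 does not support this. It speaks of burden beyond changes to axitinib itself, and an axitinib interruption is such a change.

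Finally, this is one item in a descriptive study with no hypotheses. True, but time to resolution is descriptive too, and the plan uses Kaplan-Meier there.

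**Conclusion.** The concern holds for method and direction. Section 8.7.3 names a summary that cannot accommodate open interruptions, the observation period in section 8.1 allows them, and no rule covers them. Cutting shortens the values directly. Dropping shortens the summary when duration is independent of the end of observation, and recoding as discontinuation also takes out the longer gaps.

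The size is not known. Under exponential durations with true medians of 14 to 56 days and follow-up ended only by abstraction, the completed-only median is about 1% to 28% short. Where it falls depends mainly on duration and start time, and it is negligible when both are small. The documents establish neither a particular shortfall nor that open interruptions will be common. The change is worth making because the direction is predictable and the cost is low.

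**What to change.** In section 8.7.3, define the quantity as time from halt to reinitiation. Censor interruptions still open at loss to follow-up or chart abstraction. Treat permanent discontinuation, second-line start and death as competing events, because after them a restart of the interrupted first-line treatment may never occur. Section 8.1 lists second-line start and death among the ends of observation, so the text should say explicitly that they are not ordinary censoring here.

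Report the cumulative incidence of reinitiation at fixed times, and the median only where the curve reaches 50%. With competing events it may level off below that. Give the number of interruptions still open and the number ended by each competing event. Keep the plain mean (SD) and median (IQR), labelled as describing completed interruptions only.

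State in section 8.3.4 how a halt without restart is recorded and how it is told apart from a discontinuation; the rule itself is for the sponsor to set. The eCRF needs a status for not reinitiated by the end of observation. Halt, restart and discontinuation dates are already listed. The date and reason that observation ended are not listed in section 8.3, so confirm that they are captured; the Kaplan-Meier analysis in section 8.7.4 needs them as well.

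The cost is a few sentences, slightly more analysis, and a reported duration that may be somewhat longer.

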8.7.4. Analysis of Resolution of AEs

The proportion of patients achieving resolution of AEs will be described, overall and by type and seriousness of the AEs. The time to resolution from AE onset and from initiation of management strategy will be calculated for all AEs experienced including repeated AEs. The time to resolution of AE (from the onset of AE and from the initiation of management strategies) will be separately estimated using Kaplan-Meier analysis; median time to event will be reported. Analyses will be conducted separately by type of management strategy.

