5. MILESTONES

Milestone	Planned Date
Start of data collection	30 November 2020
End of data collection	31 January 2021
Final study report	31 July 2021

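### The crude proportion of patients with resolved AEs in section 8.7.4 depends on unequal follow-up after onset; Kaplan-Meier proportions at fixed times, from the analysis already planned, would serve Objective 3 better

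*Combined protocol and SAP*

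**What the plan says.** Objective 3 (section 7) has two halves, frequency and time: "Assess the frequency of and time to AE resolution (from AE onset and initiation of management strategy, separately", and it asks for both according to management strategy.

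For frequency, section 8.7.4 plans: "The proportion of patients achieving resolution of AEs will be described, overall and by type and seriousness of the AEs". For time, it plans an estimate from AE onset and another from the start of management, "using Kaplan-Meier analysis; median time to event will be reported". It closes with: "Analyses will be conducted separately by type of management strategy".

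The window comes from section 8.1: "During the observation period, onset, management, and resolution of AEs will be assessed". Its definition is: "the time from index date to the earliest of initiation of a second line therapy, death, loss to follow-up, or date of chart abstraction".

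Section 8.2.1 sets a minimum: "Initiated axitinib/IO combination therapy at least 3 months prior to the start date of medical chart abstraction to ensure sufficient follow-up time". The limitations in section 8.9 do not mention unequal follow-up after onset.

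**The concern.** A crude proportion is easy to read when every AE is watched for the same length of time. Here an AE that starts shortly before second-line therapy, death, loss to follow-up or abstraction has little time in which to be seen to resolve, while one that starts early in a long observation period has many months. The 3-month criterion does not even this out: its clock starts at treatment initiation, and it does not stop observation from ending before abstraction.

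This matters most in the comparison by strategy. The strategies run from no action to discontinuation of axitinib with modification of the IO agent. Second-line start closes the window, and its timing could plausibly differ between them. A difference in crude proportions would then be partly a difference in follow-up. The crude proportion is the only frequency figure that the plan names for Objective 3.

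**Working it through.** The plan states no resolution rate or second-line rate, so there is no figure to reproduce. The check has two parts: what the documents fix, and an illustration on assumed rates.

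**From the documents.** The index date is in May 2019 or later (section 8.1). Data collection runs from "30 November 2020" to 31 January 2021 (section 5). The longest time from index to abstraction is therefore about 18 months (31 May 2019 to 30 November 2020) to 21 months (1 May 2019 to 31 January 2021). The shortest is 3 months (section 8.2.1). Since onset can fall anywhere on treatment and observation can end early, follow-up after onset runs from near zero to nearly that maximum.

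**Effect of follow-up alone.** If time to resolution is exponential with median m, the proportion seen to resolve within follow-up f is 1 − 2^(−f/m). For m = 3 months it is 21% at f = 1 month, 50% at 3, 75% at 6 and 98% at 18. For m = 1 month it is 50%, 88%, 98% and about 100%.

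**Illustration by simulation (2,000,000 AEs per cell).** Assumptions:
- Index-to-abstraction time is uniform on 91 to 610 days (610 days = 1 May 2019 to 31 December 2020, the middle of data collection).
- Onset is exponential with a 60-day median, and the AE is kept if onset precedes abstraction.
- Resolution is exponential with median m, and every AE would eventually resolve.
- Second-line start is exponential from onset and independent of resolution.
- Open AEs count as unresolved.

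| Crude proportion resolved | m = 14 days | m = 30 days | m = 60 days |
|---|---|---|---|
| Abstraction the only cut-off | 98.1% | 94.9% | 87.4% |
| Second-line median 365 days | 94.6% | 88.2% | 76.9% |
| Second-line median 180 days | 91.2% | 82.2% | 68.4% |
| Second-line median 90 days | 85.2% | 72.4% | 56.1% |
| True proportion resolved by day 90, 1 − 2^(−90/m) | 98.8% | 87.5% | 64.6% |

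Within a column, resolution is identical. Two strategies with second-line medians of 365 and 180 days would differ by 3.4, 6.0 or 8.5 points; with 365 and 90 days, by 9.4, 15.8 or 20.8 points; with equal medians, by 0. Kaplan-Meier at day 90 returns the bottom row within 0.1 point whichever second-line median is used.

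**Sensitivity.** If the 3 months are counted back from the study start of 30 November 2020, the minimum becomes 91 + 31 = 122 days at mid-collection. The first row is then 98.6%, 96.0% and 89.2%. With an onset median of 30 days and the 91-day minimum it is 99.1%, 96.8% and 90.3%; with 90 days, 97.4%, 93.6% and 85.5%.

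A separate simulation used slower resolution (median 3 months), treatment start 3 to 20 months before abstraction, and a median time to early end of observation of none, 12 or 6 months. The crude proportion was 79%, 68% and 59%. Kaplan-Meier at 3 months was 50% in all three.

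**Death.** Censoring at death estimates 1 − 2^(−90/m). Treating death as a competing event gives λ/(λ+h) × (1 − exp(−90(λ+h))), with λ = ln 2/m and h = −ln(S)/1826.25 per day. With S = 0.08, the 5-year survival in section 6, this is 96.3%, 83.9% and 61.4%, which is 2.5, 3.6 and 3.2 points lower. With an assumed S = 0.40 the difference is 0.9, 1.3 and 1.2 points.

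**The case against.** The plan already contains the right method. A Kaplan-Meier analysis by strategy, from two origins, will stand beside the crude proportion, and a reader can use its median to judge whether a difference reflects resolution. The study is descriptive with no hypotheses (section 8.5), so no test can go wrong. The large gaps above need second-line timing to differ strongly between strategies, and nothing in the documents shows that. With abstraction as the only cut-off, about 97% of the simulated AEs have at least 30 days of follow-up after onset and 89% have at least 90 days. The simulation also counts AEs, while section 8.7.4 counts patients, and it lets every AE eventually resolve.

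Most of this stands, and it limits the point to what is reported for frequency. It does not remove it. A median is not a frequency, and it cannot be estimated where the curve never reaches 50%.

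Some stronger readings are tempting but not supported:
- *The proportion has no time frame.* Section 8.1 supplies one, the observation period. The difficulty is that its length differs by patient.
- *The plan restricts Kaplan-Meier output to the median.* It names the median and nothing else; it does not exclude more.
- *Open AEs might be dropped, giving 100% by construction.* The natural reading counts patients with the AE in the denominator and open AEs as unresolved.

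**Conclusion.** The point holds as one of reporting. The crude proportion mixes resolution with length of follow-up after onset, and the plan names no other frequency figure for Objective 3. Its size cannot be known from the documents. On the assumptions above, with abstraction as the only cut-off, the shortfall against eventual resolution is about 2 to 5 points for AEs with a 14- to 30-day median and about 13 points for a 60-day median. Between strategies it runs from zero with equal follow-up to about 9 to 21 points in the most unequal case tried. Those gaps rest wholly on assumed second-line rates.

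A reader might infer that the comparison of strategies will be biased, or that the whole resolution analysis is unsound. Neither follows: the documents do not show that follow-up differs by strategy, and the planned Kaplan-Meier median handles unequal follow-up if censoring is non-informative. Nor does the material support insisting on a competing-risk analysis: the effect of death by day 90 is small, and it needs a different estimator from the one planned.

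**What to change.** In section 8.7.4, report Kaplan-Meier estimated proportions resolved at fixed times (for example 30 and 90 days) from AE onset, and from the start of management where there is one, by strategy and with numbers at risk. Put them beside the crude proportion or in its place.

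Censor at the end of the section 8.1 observation period, and state the assumption that this censoring is non-informative. Report by strategy how many AEs were unresolved at second-line start and how many at death. If the crude proportion is kept, label it as resolution during the observation period, state that open AEs count as unresolved, and show the median follow-up after onset next to it. A cumulative-incidence analysis with death as a competing event is optional.

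The cost is a few sentences and a little more output from an analysis already planned, with no abstraction beyond the section 8.1 window.

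The downside is that Kaplan-Meier estimates can err either way if the switch to second line depends on the course of the AE. In an assumed mix of half slow (90-day median) and half fast (14-day median) resolvers, one group switches at a median of 30 to 90 days and the other at 365. True day-90 resolution of about 74% is then estimated at 77 to 84% if slow resolvers switch sooner and 68 to 72% if fast ones do. The planned median has the same exposure (true 31 days; estimated 27 to 30 or 33 to 38), which is why the counts of AEs open at second-line start are worth having.

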8.3.3. Characterization of AEs

The following variables, to the extent they are available, will be assessed during the observation period:

- Type of AE, as defined by Common Terminology Criteria for Adverse Events (CTCAE):
 - Diarrhea, characterized by an increase in frequency and/or loose or watery bowel movements;
 - Fatigue, characterized by a state of generalized weakness with a pronounced inability to summon sufficient energy to accomplish daily activities;
 - Nausea, characterized by a queasy sensation and/or the urge to vomit;
 - Hypertension (new and worsening), characterized by a pathological increase in blood pressure;
 - Palmar-plantar erythrodysesthesia (hand-foot syndrome), characterized by redness, marked discomfort, swelling, and tingling in the palms of the hands or the soles of the feet.
- Serious AE.
 - As specified by the FDA, an AE is considered serious when the patient outcome is: death, life-threatening, hospitalization (either initial admission or prolongation of hospitalization), disability or permanent damage, or congenital anomaly/birth defect.
 - Date(s) of AE onset.
 - Date(s) of AE resolution.

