8.5. Study Size

Approximately 200 oncologists may be recruited by the physician panel vendor to abstract medical charts. AG anticipates to obtain data from the medical charts of 400-600 patients with advanced RCC. No formal sample size computation was performed as all statistical analyses are descriptive in nature and no hypotheses are being tested.

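### Kaplan-Meier for time to AE resolution leaves deaths with the AE unresolved to be censored by default, which biases the curve toward more resolution and can shorten the median

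*Combined protocol and SAP*

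**What the plan says.** Section 8.7.4 plans two kinds of resolution result. The first is a simple proportion: "The proportion of patients achieving resolution of AEs will be described, overall and by type and seriousness of the AEs". The second is time to resolution on two clocks (AE onset and start of management), which "will be separately estimated using Kaplan-Meier analysis; median time to event will be reported", separately by type of management strategy. Objective 3 in section 7 adds that these results are "stratified further by type and seriousness of AEs, as allowed by sample size".

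Section 8.1 ends observation at "the earliest of initiation of a second line therapy, death, loss to follow-up, or date of chart abstraction", and resolution is assessed only within that period.

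Section 8.3.3 states that "an AE is considered serious when the patient outcome is: death, life-threatening, hospitalization" or one of the further outcomes it lists.

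Section 8.7.4 contains no censoring rule. No section names death as a competing event or mentions a cumulative incidence estimator, and the limitations in 8.9 are silent on the point. The variable lists in 8.3.2 to 8.3.4 include neither a date of death nor the reason observation ended. Death appears there only as a criterion for seriousness.

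**The concern.** Kaplan-Meier assumes that a censored AE has the same future chance of resolving as the AEs still under observation. That is reasonable for a chart abstracted while the AE is continuing. It cannot hold for a patient who has died, because that AE will never resolve. If such patients are censored, their share of probability passes to those who resolve later, and one minus the Kaplan-Meier estimate is at or above the true cumulative incidence of resolution. The median derived from it is too short or unchanged, never too long.

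What is at stake is the time part of Objective 3. Section 6 says the study could help show that AEs associated with axitinib can be mitigated through changes to axitinib treatment, and this bias runs in the direction of that message. In a descriptive study the estimates are themselves the result, so the absence of a hypothesis test does not remove the problem.

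**Working it through.** **No figure to reproduce.** The plan states no resolution rate, death rate or expected median. Everything below is illustration under stated assumptions.

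**Set-up.** Let p be the share of AEs that end in death (from any cause) before resolution. Assume constant hazards, with total hazard scaled to 1: resolution hazard 1 − p, death hazard p.

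- Kaplan-Meier with deaths censored: resolved by t = 1 − exp(−(1 − p)t); median = ln 2/(1 − p).
- Cumulative incidence with death as a competing event: resolved by t = (1 − p)(1 − exp(−t)); median = −ln(1 − 0.5/(1 − p)), which exists only for p below 50%.

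| p | Kaplan-Meier median | Cumulative-incidence median | Ratio | Resolved at twice the Kaplan-Meier median: Kaplan-Meier | Same time: cumulative incidence |
|---|---|---|---|---|---|
| 5% | 0.730 | 0.747 | 1.024 | 75% | 73% |
| 10% | 0.770 | 0.811 | 1.053 | 75% | 71% |
| 20% | 0.866 | 0.981 | 1.132 | 75% | 66% |
| 30% | 0.990 | 1.253 | 1.265 | 75% | 60% |

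Worked line for p = 20%: ln 2/0.8 = 0.866; −ln(1 − 0.5/0.8) = −ln(0.375) = 0.981; 0.981/0.866 = 1.132.

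**In days.** With an assumed Kaplan-Meier median of 30 days, the true median is 30.7, 31.6, 34.0 and 38.0 days for the same four values of p. At day 90 Kaplan-Meier shows 87.5% resolved whatever p is; the cumulative incidence is 84.4%, 81.1%, 74.1% and 66.4%. At p = 50% the true median is not reached, yet Kaplan-Meier still reports 30 days.

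**Simulation check.** With 200,000 AEs, p = 20% and administrative censoring uniform on 90 to 600 days, Kaplan-Meier gave 87.6% resolved at day 90 and Aalen-Johansen 74.0%. The medians were 30.1 and 34.0 days.

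**Timing.** The median moves only if deaths precede it. Take 100 AEs with no other censoring, of which 20 end in death.

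- If all 20 deaths come before any resolution, Kaplan-Meier reaches 50% at the 40th resolution (0.5 × 80), when only 40 of 100 AEs have resolved. The true 50% point is the 50th resolution.
- If all 20 deaths come after the 50th resolution, the two medians are identical and only the later part of the curve differs.

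The constant-hazards ratios therefore lie between possible extremes and are not bounds.

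**Rough scale for p.** Section 6 gives 5-year survival of about 8% in advanced RCC. As a constant hazard this is −ln(0.08)/5 = 0.505 per year. If the Kaplan-Meier resolution median is 30 days, the resolution hazard is ln 2 × 365.25/30 = 8.44 per year and p = 0.505/(0.505 + 8.44), about 6%. At 90 days it is 2.81 per year and p is about 15%. This may be high for AEs as a whole, because observation also stops at second-line therapy. It would be too low for a stratum that contains fatal AEs.

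**The case against.** **Censoring at death is not written down.** This is correct. Section 8.1 says only when observation ends, and 8.7.4 gives no censoring rule. A reader might infer that the plan expressly censors deaths, but the documents do not say so. It is the default result of the two sections read together, and the plan offers no alternative.

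**The crude proportion is sound on this point.** Also correct. It counts a patient who dies unresolved as unresolved, so it would be wrong to say that all the resolution results are overstated. It does not repair the curve or median, however, because it also counts AEs still under follow-up as unresolved.

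**The promised summary is the median, and it may hardly move.** Largely correct. At p of 5% to 10% the shift is 0.7 to 1.6 days on an assumed 30-day median, and it is zero if the deaths come later. The figures at twice the median and at day 90 describe the curve, which the plan does not commit to reading at fixed times.

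**The serious stratum need not contain fatal AEs.** A reader might infer from 8.3.3 that it does so by definition. Death is one of several qualifying outcomes, so the definition admits fatal AEs without making any present. The events studied are diarrhea, fatigue, nausea, hypertension and hand-foot syndrome, and the documents do not say how many end in death. Time to resolution by seriousness is also planned only if sample size allows. Nor do the documents show that patients under particular management strategies die more often, so a claim that the bias favours certain strategies would go beyond them.

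**The study is descriptive.** Section 8.5 says "No formal sample size computation was performed as all statistical analyses are descriptive in nature and no hypotheses are being tested". This limits the severity but does not make a biased description acceptable.

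**Conclusion.** The point holds for the Kaplan-Meier curve and, when deaths occur early enough, for its median. The direction is certain if deaths are censored, which is the default reading. The size cannot be computed from the documents. Under constant hazards the true median is longer by 2%, 5%, 13% and 27% when 5%, 10%, 20% and 30% of AEs end in death. The effect is probably small for non-serious AEs. It may be material in any stratum with many deaths, and serious AEs are the likeliest example because 8.3.3 admits fatal ones. The conclusion rests on the inferred censoring rule and on assumed values for the share and timing of deaths. It does not extend to the crude proportion resolved. This is a cheap improvement, not a flaw that undermines the study.

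**What to change.** In 8.7.4:

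- State the censoring rule, and treat death with the AE unresolved as a competing event.
- Estimate the cumulative incidence of resolution by Aalen-Johansen from both AE onset and start of management.
- Report the time at which it reaches 50%, or 'not reached'.
- Tabulate the number of AEs unresolved at death, by management strategy and seriousness.

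In 8.3, add date of death and reason observation ended to the eCRF variables. The analysis cannot be run without them, and 8.1 already presupposes them. Section 8.4.1 foresees eCRF updates after the pilot test, so they fit within the existing process.

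The cost is two eCRF fields, a standard procedure in place of Kaplan-Meier, and slightly less favourable resolution figures.
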